#### 4.2.3. Part 1: Dose-Escalation

Part 1 dose escalation will characterize the safety and tolerability of escalating doses of belantamab mafodotin in combination with 200 mg pembrolizumab to establish the RP2D. In the currently ongoing FTIH study (ClinicalTrials.gov Identifier: NCT02064387), no DLTs were observed up to the highest tested dose level of 4.6 mg/kg of belantamab mafodotin and 3.4 mg/kg was selected as RP2D dose. The following dose levels of belantamab mafodotin in combination with 200 mg pembrolizumab are to be tested in this study: 2.5 mg/kg and 3.4 mg/kg (as outlined in [Figure 2](#)). Additionally, other dose levels may also be tested if emerging data suggests a beneficial risk/benefit profile at those dose levels. The RP2D from the monotherapy FTIH study (3.4 mg/kg (ClinicalTrials.gov Identifier: NCT02064387)) will not be exceeded in this combination study. During the dose escalation, at least 3 evaluable subjects will be tested per dose level, and escalation will be guided by the modified Toxicity Probability Interval (mTPI) approach.

**Figure 2 Dose Escalation Schematic for Part 1**

The mTPI design assumes the true underlying toxicity rate for maximum tolerated dose (MTD) of belantamab mafodotin falls within the range from 25% to 35% and centered at 30%. The monitoring rules for guiding dose escalations are provided in [Table 1](#). Columns provide the numbers of subjects treated at the current dose level, and rows provide the corresponding numbers of subjects experiencing toxicity. The entries of the table are dose-finding decisions (i.e., E, S, and D) representing escalating the dose, staying at the same dose, and de-escalating the dose. In addition, decision U means that the current dose level is unacceptable because of high toxicity; the current dose level and any higher dose level should be excluded from the trial. For example, when one of three subject's experiences toxicity, the decision can be located at row 1 and column 3, which is S – to stay at the current dose level. Consequently, the next cohort of subjects will be treated at the same dose level currently being used. If 0 of 3 subjects experiences toxicity, the decision is at row 0 and column 3, which is E – to escalate. Thus, the next cohort of subjects will be treated at the next-higher dose level. If three of three subjects experiences toxicity, the decision is DU – to de-escalate to the next-lower dose level, and exclude the current dose and any higher dose from the trial, because the high toxicity level is unacceptable. In dose escalation (E)/de-escalation (D), no dose skipping is allowed.

**Table 1 Dose-Escalation Monitoring Rules for Part 1 Using the mTPI Method**

Number of DLTs	Number of Subjects treated at current dose					
	1	2	3	4	5	6
0	E	E	E	E	E	E
1	D	S	S	S	S	E
2	DU	D	S	S	S	S
3		DU	DU	D		S
4			DU	DU	DU	DU
5				DU	DU	
6					DU	

The table was generated based on a beta/binomial model and precalculated before trial initiation. The letters in different colors are computed based on the decision rules under the mTPI method and represent different dose-finding actions. In addition to actions de-escalate the dose (D), stay at the same dose (S), and escalate the dose (E), the table includes action unacceptable toxicity (DU), which is defined as the execution of the dose-exclusion rule in mTPI. Excerpted from Ji et al . [\[Ji, 2010\]](#)

The DLT observation period for subjects in Part 1 is 21 days after the first dose of the study treatment. The complete safety data from DLT observation period of at least 3 subjects are needed for dose escalation decisions. Subjects who have only received belantamab mafodotin or have been withdrawn from the study for reasons other than toxicity but prior to completion of DLT observation period will be replaced.

In Part 1, dose escalation/de-escalation decisions will take into account all available safety and tolerability data. The decisions will be informed by the mTPI approach and will occur following review of these data and joint discussion by the GSK Study Team and investigators.

The dosing may be adjusted to expand any cohort to further evaluate safety at a given dose level, or to add cohorts to evaluate additional, intermediate dose levels of

GSK2858916 after discussion between GSK study team and investigators. The study procedures for these additional subject(s) or cohort(s) will be the same as that described in Section 5 and Section 7. The dose of pembrolizumab will be kept constant at 200 mg throughout the study.

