#### **4.2.3.1. Dose-Limiting Toxicity Criteria (Part 1 only)**

Any subject in Part 1 who received at least one treatment cycle of belantamab mafodotin in combination with pembrolizumab will be evaluated for DLTs.

All toxicities will be graded using National Cancer Institute (NCI) CTCAE Version 4.03 [NCI, 2010]. In addition, for belantamab mafodotin treatment related corneal events, the GSK Grading Scale (Appendix 9) should be used for evaluation of DLT.

A DLT is defined as an AE that meets at least one of the criteria defined below and is considered by the investigator to be clinically relevant and attributed (definitely, probably, or possibly) to the study therapy during the 21 day DLT observation period.

- Any Grade 4 non-hematologic toxicity
- Any Grade 3 non-hematologic toxicity, with the following exceptions (i.e., the following will not be considered a DLT): Grade 3 diarrhea, nausea or vomiting that responds to standard of care within 72 hours; Grade 3 hypertension (controlled following addition of 1 antihypertensive medication); and Grade 3 tumor lysis syndrome
- Any Grade 3 or greater non-hematologic laboratory value if either:
  - The laboratory abnormality persists for >48 hrs despite supportive treatment or,
  - The abnormality leads to hospitalization
- Hematologic toxicity:
  - Grade 4 hematologic toxicity lasting  $\geq$  7 days, except thrombocytopenia:
    - Grade 4 thrombocytopenia of any duration
    - Grade 3 thrombocytopenia associated with clinically significant bleeding
  - Grade 3 or greater febrile neutropenia lasting >48 hours despite adequate treatment:

CCI - This section contained Clinical Outcome Assessment data collection questionnaires or indices, which are protected by third party copyright laws and therefore have been excluded.

- Nephrotoxicity requiring dialysis, and is not considered to be due to disease under study (i.e., myeloma) based on investigator's assessment
- Liver toxicity meeting pre-specified GSK liver stopping criteria (see Section 5.4.1.1)
- Prolonged delay (>14 days) in initiating Cycle 2 due to any treatment (pembrolizumab or belantamab mafodotin) related toxicity, with the exception of Grade 1-2 corneal events (GSK grading scale for belantamab mafodotin treatment related corneal events; Table 17)
- Any treatment-related toxicity that causes the subject to discontinue treatment during Cycle 1

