## 9.4. Data Analysis Considerations

### 9.4.1. Analysis Populations

**All Treated Population:** will consist of all subjects who received at least one dose of study drug(s). Safety and clinical activity data will be evaluated based on this population.

**The Pharmacokinetic Population:** This will consist of those subjects in All Treated Subjects Population from whom at least one PK sample is obtained and analyzed.

**DLT Evaluable Population:** will consist of subjects fulfilling the 'All Treated' population criteria during part 1 (Dose Escalation) and are followed up for a 21-day period or withdrawn within 21 days due to an AE meeting the definition of a DLT as defined in Section 4.2.3.1.

**All Evaluable Population:** This is the population used for decision-making at the futility analysis during part 2 (Expansion Cohort). This will be the population for Bayesian predictive adaptive design as defined in Section 9.5.2 and summaries of response if data warrant. In general, subjects are evaluable if they have received at least 1 dose of treatment for both drugs and the time from the first dose to the time of data cut-off is more than 66 days, i.e., reached the time of three planned disease assessments. Details on deriving the evaluable population will be provided in the RAP.

Additional analysis populations may be defined in the Reporting and Analysis Plan (RAP).

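### The protocol gives conflicting rules on whose DLT enters the mTPI count, and one DLT criterion can be met only after the 21-day window has closed

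*Protocol*

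**What the plan says.** **Replacement.** Section 4.2.3, in the text under Table 1, replaces two groups: "Subjects who have only received belantamab mafodotin or have been withdrawn from the study for reasons other than toxicity" but before DLT observation was complete. The synopsis (Part 1: Dose Escalation) carries the same rule. Neither states an exception for a subject who received only belantamab mafodotin because of a DLT.

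**Who is assessed.** Section 4.2.3.1 says: "Any subject in Part 1 who received at least one treatment cycle of belantamab mafodotin in combination with pembrolizumab will be evaluated for DLTs". The synopsis agrees. The same section also lists, as a DLT, treatment-related toxicity that makes the subject stop during Cycle 1.

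**Analysis population.** Section 9.4.1 builds the DLT Evaluable Population on All Treated (at least one dose of study drug) in Part 1. It takes those who "are followed up for a 21-day period or withdrawn within 21 days due to an AE meeting the definition of a DLT". Having received both drugs is not a condition.

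**Window and delay criterion.** "The DLT observation period for subjects in Part 1 is 21 days after the first dose of the study treatment", and escalation needs complete data from that period for at least 3 subjects. Section 4.2.3.1 ties the DLT definition to the same 21 days, yet lists as a DLT: "Prolonged delay (>14 days) in initiating Cycle 2 due to any treatment (pembrolizumab or belantamab mafodotin) related toxicity" (Grade 1-2 corneal events excepted). Another item says that dose-limiting toxicity after 21 days is considered in choosing the expansion dose.

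**The concern.** The protocol's own rules can produce a subject who has a DLT and never receives pembrolizumab. Belantamab mafodotin goes first, and pembrolizumab is skipped if an infusion reaction does not recover within the +3-day window (4.2.1). A Grade 4 reaction leads to permanent withdrawal (5.4.1.8). Grade 3 and Grade 4 non-hematologic toxicities are DLTs, and infusion reactions are not among the listed Grade 3 exceptions. That subject counts under 9.4.1. Under 4.2.3 and 4.2.3.1 the same subject can be replaced and left unassessed.

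The second gap concerns timing. Some holds may become DLTs only through the delay criterion. Table 4 withholds treatment for Grade 3 thrombocytopenia on a dosing day, but 4.2.3.1 makes this a DLT only with clinically significant bleeding. Non-febrile Grade 3 neutropenia on Day 1 is also withheld and, in the unredacted text, matches no other specific criterion.

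Table 1 acts on very small counts. At its cohort sizes one DLT more or less changes the instruction, so it must be clear which DLTs are counted, and when.

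**Working it through.** **Step 1: reproduce the plan's decisions.** The inputs from section 4.2.3 are a toxicity rate at the MTD that "falls within the range from 25% to 35% and centered at 30" percent, and two worked examples. "If 0 of 3 subjects experiences toxicity, the decision is at row 0 and column 3", which is Escalate. For 1 of 3, "the decision can be located at row 1 and column 3, which is S" (Stay). The prior and the exclusion cut-off are not stated. I assumed Beta(1,1), and exclusion if P(p > 0.30) exceeds 0.95.

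The posterior is Beta(1+x, 1+n−x). The unit probability mass of an interval is its posterior probability divided by its width, over 0-0.25 (E), 0.25-0.35 (S) and 0.35-1 (D). The largest value decides.

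| DLTs/n | E | S | D | Decision |
|---|---|---|---|---|
| 0/3 | 2.734 | 1.379 | 0.275 | Escalate |
| 1/3 | 1.047 | 1.753 | 0.866 | Stay |
| 1/6 | 2.220 | 2.111 | 0.360 | Escalate |

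The same calculation gives Stay for 2/6 and for 1/4. Rows 0 and 1 of Table 1 (all E; and D S S S S E) are reproduced in full. Of three priors tried, Beta(1,1), Beta(0.5,0.5) and Beta(0.005,0.005), only Beta(1,1) matches row 1. The lower rows look shifted in the extracted text, and I do not rely on them beyond 2/6, which reads S there too.

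**Step 2: one subject under the two definitions.** Take three treated subjects, one with a DLT that prevented pembrolizumab.

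- Section 9.4.1: the subject is kept, 1/3, Stay.
- Sections 4.2.3 and 4.2.3.1, read literally, with a DLT-free replacement: 0/3, Escalate.
- DLT kept and one DLT-free subject added: 1/4, Stay.

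At six subjects, 2/6 reads Stay and 1/6 reads Escalate.

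**Step 3: timing of the delay criterion.** Cycles last 21 days, so Cycle 2 is due on Day 1 + 21 = Day 22. A delay of more than 14 days is at least 15 days: Day 22 + 15 = Day 37. The window and the minimum escalation data end about 15 days earlier. The RP2D analysis (synopsis; 9.5.1) is also placed after the last cohort's DLT period.

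**Step 4: possible size.** The share of DLTs affected is not in the documents. I assume 10%, 25% or 50%, for illustration only. With true DLT rate p, P(0/3) = (1−p)³.

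- If a share f of DLT subjects is dropped and replaced, p′ = p(1−f)/(1−pf). For p = 0.40 and f = 0.25, p′ = 0.30/0.90 = 0.333 and P(0/3) = 0.667³ = 29.6%.
- If a share g of DLTs is not yet counted but the subjects stay in, p″ = p(1−g). For p = 0.40 and g = 0.25, p″ = 0.30 and P(0/3) = 0.70³ = 34.3%.

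P(0/3), which reads Escalate:

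| True rate | All counted | Dropped and replaced: 10 / 25 / 50% | Not yet counted: 10 / 25 / 50% |
|---|---|---|---|
| 30% | 34.3% | 37.6 / 43.3 / 55.9% | 38.9 / 46.5 / 61.4% |
| 40% | 21.6% | 24.4 / 29.6 / 42.2% | 26.2 / 34.3 / 51.2% |
| 50% | 12.5% | 14.6 / 18.7 / 29.6% | 16.6 / 24.4 / 42.2% |

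At n = 6 and a true rate of 40%, the chance of at most 1 DLT (Escalate) is 23.3% with all counted, 35.1% with 25% dropped and replaced, and 53.4% with 50%.

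**The case against.** A reader might infer that the design removes exactly the subjects whose toxicity stopped dosing, and so biases the DLT rate downward. The documents do not support that.

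- Section 9.4.1 is the only formal definition of the DLT Evaluable Population, and it keeps these subjects. In 4.2.3, the words about reasons other than toxicity can be read as covering both groups, which would agree with 9.4.1.
- Table 1's columns are subjects treated at the current dose. Replacement need not mean that the DLT is deleted; if it is kept, the count is 1/4 and the decision is Stay.
- A subject who received both drugs and was withdrawn for toxicity is not replaced. Only DLTs arising before pembrolizumab are at issue, and most infusion reactions to date were Grade 1-2 (Table 2).
- No section says that a subject on hold is scored as free of DLT. The toxicity behind a delay may already be a DLT within the window, and the investigator and Medical Monitor may designate any other event as one.
- Escalation also rests on all available safety data and joint discussion. The planned escalation is one step, from 2.5 to 3.4 mg/kg, and 3.4 mg/kg may not be exceeded.

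All of this stands, and it narrows the point. It does not settle which count enters Table 1. The more favourable reading of the replacement sentence leaves the condition of at least one combination cycle in 4.2.3.1. That condition also sits badly with the section's own criterion of discontinuation during Cycle 1. The late-toxicity item concerns the expansion dose, not the Table 1 count.

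**Conclusion.** The point holds as an internal contradiction plus a timing gap, not as a demonstrated bias. Section 9.4.1 counts a subject whose DLT after belantamab mafodotin prevents pembrolizumab; 4.2.3, 4.2.3.1 and the synopsis allow the same subject to be dropped and replaced. The Cycle 2 delay criterion can be met only from about Day 37, against a 21-day definition and decision point.

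One DLT left out, with a DLT-free replacement, turns Stay (1/3) into Escalate (0/3). A count of 1/6 in place of 2/6 does the same. These decisions agree with Table 1 and do not depend on the assumed share. The probabilities in Step 4 do depend on it, so they show sensitivity and are not estimates. Joint review of all safety data limits the harm. The correction is still worth making because the rule governs dose escalation and the change is cheap.

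**What to change.** 1. Reconcile section 4.2.3 (text under Table 1), section 4.2.3.1 and the corresponding synopsis text with the DLT Evaluable Population in 9.4.1. One definition, which does not remove a subject because of a DLT, should supply both the numerator and the denominator for Table 1.
2. Reconcile the 21-day window with the Cycle 2 delay criterion. State how a subject whose Cycle 2 is on hold for toxicity enters Table 1 when the escalation decision is taken.

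Neither change requires a new dose or a new toxicity criterion. The cost is wording and, depending on how the second item is resolved, possibly about two weeks' wait in a cohort where such a hold is in progress.

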#### **4.2.3.1. Dose-Limiting Toxicity Criteria (Part 1 only)**

Any subject in Part 1 who received at least one treatment cycle of belantamab mafodotin in combination with pembrolizumab will be evaluated for DLTs.

All toxicities will be graded using National Cancer Institute (NCI) CTCAE Version 4.03 [NCI, 2010]. In addition, for belantamab mafodotin treatment related corneal events, the GSK Grading Scale (Appendix 9) should be used for evaluation of DLT.

A DLT is defined as an AE that meets at least one of the criteria defined below and is considered by the investigator to be clinically relevant and attributed (definitely, probably, or possibly) to the study therapy during the 21 day DLT observation period.

- Any Grade 4 non-hematologic toxicity
- Any Grade 3 non-hematologic toxicity, with the following exceptions (i.e., the following will not be considered a DLT): Grade 3 diarrhea, nausea or vomiting that responds to standard of care within 72 hours; Grade 3 hypertension (controlled following addition of 1 antihypertensive medication); and Grade 3 tumor lysis syndrome
- Any Grade 3 or greater non-hematologic laboratory value if either:
  - The laboratory abnormality persists for >48 hrs despite supportive treatment or,
  - The abnormality leads to hospitalization
- Hematologic toxicity:
  - Grade 4 hematologic toxicity lasting  $\geq$  7 days, except thrombocytopenia:
    - Grade 4 thrombocytopenia of any duration
    - Grade 3 thrombocytopenia associated with clinically significant bleeding
  - Grade 3 or greater febrile neutropenia lasting >48 hours despite adequate treatment:

CCI - This section contained Clinical Outcome Assessment data collection questionnaires or indices, which are protected by third party copyright laws and therefore have been excluded.

- Nephrotoxicity requiring dialysis, and is not considered to be due to disease under study (i.e., myeloma) based on investigator's assessment
- Liver toxicity meeting pre-specified GSK liver stopping criteria (see Section 5.4.1.1)
- Prolonged delay (>14 days) in initiating Cycle 2 due to any treatment (pembrolizumab or belantamab mafodotin) related toxicity, with the exception of Grade 1-2 corneal events (GSK grading scale for belantamab mafodotin treatment related corneal events; Table 17)
- Any treatment-related toxicity that causes the subject to discontinue treatment during Cycle 1

- Any other toxicity considered to be dose-limiting that occurs beyond 21 days will be considered in the selection of the dose to recommend for expansion cohorts
- Any other event which in the judgment of the investigator and GSK Medical Monitor is considered to be a DLT

A subject who develops a DLT will be allowed to continue on study treatment if the toxicity did not meet predefined stopping criteria (Section 5.4) and recovered to  $\leq$  Grade 1 within 14 days, if the investigator and medical monitor agree that for a given subject the potential benefits may outweigh the risks.

#### **4.2.3.2. Completion of Dose Escalation and the Recommended Phase 2 Dose (RP2D)**

The dose escalation will complete when RP2D is determined. A dose level at or below the pre-specified max dose of 3.4 mg/kg may be selected as RP2D in combination with the fixed dose of 200 mg pembrolizumab. All available data from Part 1 will be analyzed. The totality of the data including, but not be limited to, safety, available PK profile, and observed signs of clinical activity will be considered for the RP2D selection of belantamab mafodotin to be administered in combination with pembrolizumab. If necessary, alternative doses and schedules can be explored to determine additional clinically active regimens.

Once the RP2D has been identified, an expansion cohort (Part 2) will open for enrollment of up to 28 subjects with RRMM in order to confirm the safety profile and to evaluate the clinical activity of the combination.

If necessary, alternative schedules and/or additional dose(s) of belantamab mafodotin can be explored after RP2D is identified.

### **4.3. Type and Number of Subjects**

The study will enroll adult subjects with RRMM, who have undergone stem cell transplant, or are considered transplant ineligible, and who have been previously treated with at least 3 prior lines that include the following: an immunomodulatory agent (i.e. lenalidomide or pomalidomide), proteasome inhibitor (i.e. bortezomib, ixazomib or carfilzomib) and an anti-CD38 antibody alone or in combination. Line of therapy are defined by consensus panel of the International Myeloma Workshop [Rajkumar, 2011].

Overall, it is estimated that up to 40 evaluable subjects will be enrolled in this two-part study (up to 12 in Part 1, and 28 in Part 2).

### **4.4. Design Justification**

This is the first clinical study in which belantamab mafodotin will be administered in combination with pembrolizumab. Therefore, a two-part study design is implemented to allow for careful safety assessments during dose escalation. Part 1 will consist of dose escalation to establish the RP2D of belantamab mafodotin in combination with 200 mg of pembrolizumab. Once RP2D has been established, Part 2 will enroll an additional 28 subjects with RRMM to further confirm safety and to assess the clinical activity of the

combination at the RP2D of belantamab mafodotin. Futility analyses will be conducted from when response data is available from 10 subjects. Details of the futility analysis are described in Section 9.5.2.

## 4.5. Dose Justification

### 4.5.1. Belantamab Mafodotin Starting Dose Justification

The starting dose for belantamab mafodotin will be 2.5 mg/kg administered intravenously Q3W on Day 1 of each 21-day Cycle. Careful dose escalation and monitoring will be implemented to protect subjects' safety throughout the study.

The 2.5 mg/kg dose is considered to be appropriate starting dose for combination with a fixed dose of 200 mg pembrolizumab:

- The starting dose of 2.5 mg/kg is one dose level below the 3.4 mg/kg, which had an acceptable safety profile in FTIH trial;
- Per currently available data, it is anticipated that the starting dose of 2.5 mg/kg will be well tolerated and is not expected to result in an excessive toxicity;
- Based on the non-specific clearance mechanism with large capacity of both: belantamab mafodotin and pembrolizumab, the likelihood for drug-drug interactions from combining belantamab mafodotin with pembrolizumab is low.

### 4.5.2. Pembrolizumab Dose Justification

The dose of pembrolizumab for this study is 200 mg every 3 weeks (Q3W). Based on the totality of data generated in the Keytruda development program, 200 mg Q3W is the appropriate dose of pembrolizumab for adults across all indications. As outlined below, this dose is justified by:

- Clinical data from 8 randomized studies in melanoma and NSCLC indications demonstrating flat dose- and exposure-efficacy relationships from 2 mg/kg Q3W to 10 mg/kg every 2 weeks (Q2W), representing an approximate 5 to 7 fold exposure range (refer to the IB) [Keytruda IB, 2021].
- Population PK analysis showing that both fixed dosing and weight-based dosing provides similar control of PK variability with considerable overlap in the distributions of exposures, supporting suitability of 200 mg Q3W.
- Clinical data showing meaningful improvement in benefit-risk including overall survival at 200 mg Q3W across multiple indications, and
- Pharmacology data showing full target saturation in both systemic circulation (inferred from PK data) and tumor (inferred from physiologically-based PK [PBPK] analysis) at 200 mg Q3W.

Among the 8 randomized dose-comparison studies, a total of 2262 subjects were enrolled with melanoma and non-small cell lung cancer (NSCLC), covering different disease settings (treatment naïve, previously treated, PD-L1 enriched, and all-comers) and different treatment settings (monotherapy and in combination with chemotherapy). Five studies compared 2 mg/kg Q3W versus 10 mg/kg Q2W (KN001 Cohort B2, KN001 Cohort D, KN002, KN010, and KN021), and 3 studies compared 10 mg/kg Q3W versus 10 mg/kg

Q2W (KN001 Cohort B3, KN001 Cohort F2 and KN006). All of these studies demonstrated flat dose- and exposure-response relationships across the doses studied representing an approximate 5- to 7.5-fold difference in exposure. The 2 mg/kg (or 200 mg fixed-dose) Q3W provided similar responses to the highest doses studied. Subsequently, flat dose-exposure-response relationships were also observed in other tumor types including head and neck cancer, bladder cancer, gastric cancer and classical Hodgkin Lymphoma, confirming 200 mg Q3W as the appropriate dose independent of the tumor type. These findings are consistent with the mechanism of action of pembrolizumab, which acts by interaction with immune cells, and not via direct binding to cancer cells.

Additionally, pharmacology data clearly show target saturation at 200 mg Q3W. First, PK data in KN001 evaluating target-mediated drug disposition (TMDD) conclusively demonstrated saturation of PD-1 in systemic circulation at doses much lower than 200 mg Q3W. Second, a PBPK analysis was conducted to predict tumor PD-1 saturation over a wide range of tumor penetration and PD-1 expression. This evaluation concluded that pembrolizumab at 200 mg Q3W achieves full PD-1 saturation in both blood and tumor.

Finally, population PK analysis of pembrolizumab, which characterized the influence of body weight and other subject covariates on exposure, has shown that the fixed-dosing provides similar control of PK variability as weight based dosing, with considerable overlap in the distribution of exposures from the 200 mg Q3W fixed dose and 2 mg/kg Q3W dose. Supported by these PK characteristics, and given that fixed-dose has advantages of reduced dosing complexity and reduced potential of dosing errors, the 200 mg Q3W fixed-dose was selected for evaluation across all pembrolizumab protocols.

